2.1.2 Prior and Concomitant medications

Prior medications are those the patient used prior to the first IMP intake. Prior medications can be discontinued before first administration or can be ongoing during treatment phase.

Concomitant medication is any treatment received by the patient at the same time as the IMP treatment, from 1st IMP injection up to last IMP injection + 1 day (0 day for anti-diabetic therapy) whichever comes earlier.

All medications will be coded using the most current version of World Health Organization-Drug Dictionary (WHO-DD) at the time of each database lock.

Prohibited concomitant medication is limited to drugs contraindicated with use of basal insulin as per drug labels.

2.1.3 Efficacy endpoints

HbA1c and FPG will be measured by central laboratory. Blood sample taken used for analyses are those collected at baseline, Month 6, Month 12 or premature EOT. Analysis time point will be either the nominal visit or the reallocated visit (reallocation process is described in [Section 2.5.4](#)).

For patients randomized and not treated, the baseline value is defined as the last available value obtained up to the date and time of randomization.

Observation period of efficacy variables

- The **12-month randomized period** is defined as the time from randomization up to Day 360 (Visit 4). It includes the extension period (after Day 180 [Visit 3] to Day 360 [Visit 4]) to allow for collection of additional endpoint data such as health care utilization².

- The **6-month randomized period** is defined as the time from randomization up to Day 180 (Visit 3) or date of end of study whichever come earlier¹.
- The **6-month on-treatment period** is defined as the time from 1st IMP intake up to Day 180 (Visit 3) or date of last IMP + 1 day (7 days for HbA1c), whichever comes earlier¹.
- The **6 to 12-month randomized period** named “from start of Month 7 to Month 12” is defined as the time from the day following the 6-month randomized treatment period up to the end of the 12-month randomized period².

1. Used at time of 6 month database lock.
2. Used at time of 12 month database lock.

2.1.3.1 Primary efficacy endpoint(s)

The primary efficacy endpoint is the proportion of patients with individualized HbA1c target attainment per HEDIS criteria assessed at randomization without documented symptomatic ($BG \leq 70$ mg/dL) or severe hypoglycemia at any time of day from baseline to 6 months.

The individual components of individualized HbA1c target attainment and absence of any documented symptomatic ($BG \leq 70$ mg/dL) or severe hypoglycemia will also be evaluated as supportive analyses to evaluate consistency:

- Proportion of patients with individualized HbA1c target attainment at 6 months, and,
- Proportion of patients without documented symptomatic ($BG \leq 70$ mg/dL) or severe hypoglycemia.

2.1.3.2 Secondary efficacy endpoint(s)

- Change in HbA1c from baseline (obtained at screening visit within one week of study initiation) to 6 months,
- Proportion of patients who remain on assigned basal insulin therapy (persistent with assigned therapy) at 6 and 12 months,
- Proportion of patients with individualized HbA1c target attainment per HEDIS criteria at 6 months without documented symptomatic ($BG < 54$ mg/dL) or severe hypoglycemia at any time of day from baseline to 6 months,
- Proportion of patients with individualized HbA1c target attainment per HEDIS criteria at 12 months without documented symptomatic ($BG < 54$ mg/dL) or severe hypoglycemia at any time of day from baseline to 12 months, and,
- Proportion of patients with individualized HbA1c target attainment (per HEDIS criteria) at 12 months without documented symptomatic ($BG \leq 70$ mg/dL) or severe hypoglycemia at any time of day from baseline to 12 months.

2.1.3.3 Other efficacy endpoint(s)

- Change in HbA1c from baseline to 12 months,
- Change in FPG from baseline to 6 months and 12 months,
- Change in body weight from baseline to 6 months and 12 months,

- Basal insulin dose collected at the study visit on the e-CRF at 6 and 12 months,
- Proportion of patients with HbA1c <8% at 6 months without documented symptomatic (BG ≤70 mg/dL) or severe hypoglycemia,
- Proportion of patients with HbA1c <7% at 6 months without documented symptomatic (BG ≤70 mg/dL) or severe hypoglycemia,
- Proportion of patients with HbA1c <8% at 6 months, and,
- Proportion of patients with HbA1c <7% at 6 months.

2.1.4 Safety endpoints

The following safety parameters will be analyzed in the clinical study report:

- Hypoglycemia (according to American Diabetes Association [ADA] Workgroup on Hypoglycemia) (2),
- AEs, SAEs,
- Injection site reactions,
- Hypersensitivity reactions,
- Vital signs, and,
- Healthcare resource utilization including hospitalizations and emergency department or other provider visits and healthcare costs.

Observation period for safety endpoints

- The **pre-treatment period** is defined as the time from informed consent up to the time of the first injection of IMP.
- The **12-month on-treatment period** is defined as the time from the 1st IMP intake up to 1 day after the trial is completed².
- The **6-month on-treatment period** named “Month 1 to Month 6” is defined as the time from 1st IMP intake up to Day 180 (Visit 3) or 1 day after date of last insulin (either IMP or commercial basal insulin prescribed following a switch) or 6-month visit, whichever comes earlier³.
- The **6 to 12-month on-treatment period** named “from start of Month 7 to Month 12” is defined as the time from the day following the 6-month on-treatment period up to the end of the 12-month on-treatment period².
- The **post-treatment period** is defined as the time starting 2 days after last injection of IMP (after the on-treatment period).
- The **on-study observation period** is defined as the time from randomization until the end of the study (defined as last protocol planned visit or the resolution/stabilization of all SAEs and AE with pre-specified monitoring).

2. Used at time of 12 month database lock,

3. Used for 6 month and 12 month database lock.

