9.2.3 Safety endpoints

The following safety parameters will be analyzed in the clinical study report:

- Hypoglycemia (according to ADA Workgroup on Hypoglycemia),
- Adverse events, serious adverse events,
- Injection site reactions,
- Hypersensitivity reactions,
- Vital signs.

Hypoglycemia endpoints will be classified in categories ([Section 9.2.3.1](#)) after events have been characterized using ADA Working group.

- Incidence of documented symptomatic ($BG \leq 70$ mg/dl) nocturnal (0000-0559) hypoglycemia from baseline to 6 and 12 months, and 24-hour hypoglycemia from baseline to 12 months
- Rate of documented symptomatic ($BG \leq 70$ mg/dl) hypoglycemia (24 hour and nocturnal) from baseline to 6 and 12 months
- Incidence and rate of documented symptomatic ($BG < 54$) hypoglycemia (24 hour and nocturnal) from baseline to 6 and 12 months
- Incidence and rate of severe hypoglycemia (24 hour, per ADA definition) from baseline to 6 and 12 months

The observation period of safety data is divided into 3 main categories:

- The pre-treatment period is defined as the time from informed consent up to the time of the first injection of IMP
- The on-treatment period of the whole study is defined as the time from the first injection of IMP up to 1 day after the last injection of IMP
- The 6-month on-treatment period is defined as the time from first injection of IMP up to Week 26 (Visit 8) or up to 1 day after the last injection of IMP whichever comes earlier
- The post-treatment period is defined as the time starting 1 day after last injection of IMP (after the on-treatment period)

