11.4.3 Analyses of safety data

The summary of safety and tolerance results will be presented by treatment group (Section 9.2.3).

All safety analyses will be performed on the Safety population using the following common rules:

- The baseline value is defined as the last available value prior to the first injection of IMP,
- There are no pre-defined Potentially Clinically Significant Abnormality (PCSA) values for this study,
- There are no safety endpoints which are adjudicated.

The baseline values for all safety analyses are defined as the last available value prior to the first dose of randomized treatment. There are no quantitative safety parameters based on central laboratory measurements. The last on-treatment value is defined as the value collected at the same day/time of the last dose of randomized product. If this value is missing, this on-treatment value is the closest one prior to the last dose intake. Given the short half-life for duration of action of insulin, the TEAE reporting period is one day after last administration of IMP.

The analysis of the safety variables is essentially descriptive and no systematic testing is planned. Relative risk for the Toujeo arm of the study versus the comparator basal insulins group, and their 95% CI may be provided, if relevant.

Hypoglycemia

The incidence of hypoglycemia will be analyzed using logistic regression, adjusting for randomization strata and other baseline characteristics as clinically appropriate and if the model permits. The rate per patient-year of hypoglycemic events will be analyzed using an over-dispersed Poisson regression model, adjusting for randomization strata and other baseline characteristics as clinically appropriate and if the model permits.

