1.5 MODIFICATIONS TO THE STATISTICAL SECTION OF THE PROTOCOL

In the protocol (1) Section 11.4.2, Analyses of efficacy endpoints, defines the analysis of HbA1c endpoints (change from baseline to 6 months) and self-reported satisfaction score using a mixed-effect model with repeated measures (MMRM) approach under the missing at random (MAR) framework, using an adequate contrast at Month 6. Since at the time of the 6 month database lock, only baseline and 6 month HbA1c data are available, an analysis of covariance (ANCOVA) will be performed at time of 6 month database lock and a MMRM at time of 12 month database lock.

In the protocol (1) Section 11.4.2, Analysis of primary efficacy endpoint(s), exploratory analysis for primary endpoint was modified. The Predictive Enrichment method is replaced by Subgroup Identification Based on Difference Effect Search (SIDES). The rationale is that the predictive enrichment procedure does not adjust for multiplicity. Additionally, the definition of subgroups is based on a score, defined as a function of multiple covariates, which makes difficult the clinical interpretation. On the other side, SIDES method uses fewer covariates (ie, 2 or 3 covariates), that is easier to interpret from a clinical point of view. Additionally, SIDES corrects for multiplicity.

As mentioned in Clinical Trial Protocol Amendment No. 01, an IA is planned when 1800 patients have completed their 6 month visit. The calculation takes into account one IA using a group sequential approach with an efficacy boundary based on a gamma (-3) alpha spending function.

The cut-off date for the IA is the date when 1800 patients have completed their 6 month visit.

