2.4.5 Analyses of safety endpoints

The summary of safety and tolerance results will be presented by treatment group.

All safety analyses will be performed on the safety population using the following common rules:

- The baseline value is defined as the last available value prior to the first injection of IMP,
- There are no safety endpoints which are adjudicated.

The baseline values for all safety analyses are defined as the last available value prior to the first dose of randomized treatment. Given the short half-life for duration of action of insulin, the TEAE reporting period is up to one day after last administration of IMP.

The analysis of the safety variables is essentially descriptive and no systematic testing is planned.

In addition, for hypoglycemia events, relative risks and odd-ratios with their associated 95% CI will be provided.

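### SAP 2.1.4 ends the 12-month on-treatment period at trial completion, while SAP 2.4.5, the protocol and the SAP's own post-treatment period are tied to last IMP

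*SAP*

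**What the plan says.** **12-month safety window.** SAP 2.1.4 states that this period "is defined as the time from the 1st IMP intake up to 1 day after the trial is completed". SAP 2.1.4.1 and 2.1.4.2 define treatment-emergent hypoglycemia and TEAEs by it. SAP 2.4.5.1 names it for the hypoglycemia analyses at the 12-month lock.

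**Everything tied to last IMP.** Protocol 9.2.3 defines whole-study on-treatment time as the "time from the first injection of IMP up to 1 day after the last injection of IMP". Protocol 11.4.3 says "the TEAE reporting period is one day after last administration of IMP", and SAP 2.4.5 repeats it: "the TEAE reporting period is up to one day after last administration of IMP". The post-treatment period in SAP 2.1.4 starts two days after the last IMP injection, with a parenthesis placing it after the on-treatment period.

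**6-month safety window.** Protocol 9.2.3 runs it "up to Week 26 (Visit 8) or up to 1 day after the last injection of IMP whichever comes earlier". SAP 2.1.4 uses a different limit, "1 day after date of last insulin (either IMP or commercial basal insulin prescribed following a switch", or Visit 3 if that is earlier.

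**Month 7-12 window.** SAP 2.1.4 says it "is defined as the time from the day following the 6-month on-treatment period up to the end of the 12-month on-treatment period".

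**Follow-up after stopping.** Under Protocol 10.3.3 to 10.3.5, patients who stop IMP keep reporting hypoglycemia, return at Day 180 and are encouraged to continue to Day 360.

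**The concern.** A patient who stops IMP early and stays in follow-up has a long stretch off IMP. Under SAP 2.1.4 that stretch is on-treatment. Under SAP 2.4.5 and the protocol it is not. A programmer cannot satisfy both, and the SAP does not say which rule prevails.

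If the 2.1.4 wording is used, TEAE counts, hypoglycemia incidence and the person-time behind the hypoglycemia rates at the 12-month lock all include time off the study insulin. SAP 2.4.5.1 uses the log of the on-treatment duration as the offset in the rate model, so the window enters that model directly. The on-treatment and post-treatment periods would also overlap, and the same event could be classified differently at the two locks. Hypoglycemia risk at 6 and 12 months is a secondary objective, so the window should not be left to be settled at programming in an open-label trial.

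**Working it through.** The plan gives no figure that depends on this definition, so the check is a comparison of texts followed by day counts.

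**1. Which wording is the exception?** SAP 2.1.4.1, 2.1.4.2 and 2.4.5.1 name the 12-month period without restating its end. The trial-completion end is written once, in SAP 2.1.4. Last IMP plus one day is written in Protocol 9.2.3, Protocol 11.4.3 and SAP 2.4.5, and SAP 2.1.2 uses it for concomitant medication other than anti-diabetic therapy. A post-treatment period starting at last IMP plus two days follows on exactly only if on-treatment time ends at last IMP plus one. The SAP 2.1.4 phrase is therefore the exception.

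**2. Day counts for one patient.** Assumptions: first dose on Day 1, last IMP on Day d, last visit on Day 360.
- Last-IMP rule: on-treatment days = d + 1.
- SAP 2.1.4 as written: on-treatment days = 360 + 1 = 361.
- Off-IMP days counted as on-treatment = 361 − (d + 1).
- Post-treatment starts on Day d + 2, so all of these off-IMP days are also post-treatment.

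| Last IMP (Day) | Last-IMP rule | SAP 2.1.4 | Off-IMP days counted | Share of 361 |
|---|---|---|---|---|
| 30 | 31 | 361 | 330 | 91% |
| 60 | 61 | 361 | 300 | 83% |
| 120 | 121 | 361 | 240 | 66% |
| 180 | 181 | 361 | 180 | 50% |
| 270 | 271 | 361 | 90 | 25% |
| 360 | 361 | 361 | 0 | 0% |

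For d = 60 the doubly classified days are Day 62 to Day 361. If the parenthesis in the post-treatment definition governs instead, that period starts on Day 362, after the last visit. The post-treatment tables planned in SAP 2.4.5.2 would then be almost empty.

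**3. The two locks.** Suppose this patient takes no basal insulin after Day 60. The 6-month window ends on Day 61, so an AE on Day 100 is post-treatment at the 6-month lock. With the SAP 2.1.4 window it is treatment-emergent at the 12-month lock. The Month 7-12 period would run from Day 62 to Day 361, which is 300 days. Of these, 180 − 62 + 1 = 119 days (40%) are on or before Day 180.

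**4. The 6-month limit.** Now suppose the patient stops IMP on Day 60, switches to commercial basal insulin and stays on it, with Visit 3 on Day 180. Protocol 9.2.3 ends the 6-month window on Day 61. SAP 2.1.4 ends it on Day 180. The SAP's post-treatment period, counted from last IMP, still starts on Day 62.

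**5. Size across a trial arm.** The documents give no stopping rate, so a range is assumed. If a share w stops on Day s and stays to Day 360, mean on-treatment time under the last-IMP rule is (1 − w) × 361 + w × (s + 1).
- w = 5%, s = 180: 352.0 days; 361/352.0 gives 2.6% more person-time under SAP 2.1.4.
- w = 10%: 343.0 days (s = 180) or 334.0 days (s = 90), so 5.2% or 8.1% more.
- w = 20%: 325.0 or 307.0 days, so 11.1% or 17.6% more.
- w = 30%, s = 90: 280.0 days, so 28.9% more.

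**6. Effect on the hypoglycemia rate ratio.** Assumed: on-IMP rates of 1.6 and 2.0 events per patient-year (ratio 0.80), and stopping at 40% of the year. The off-IMP share of time is then 0.6w, and the apparent rate is r(1 − 0.6w) + s′(0.6w), where s′ is the off-IMP rate.
- w = 20% in both arms: s′ = 0 gives 1.408/1.760 = 0.80; s′ = 0.5 gives 1.468/1.820 = 0.81.
- w = 30% in both arms: s′ = 0 gives 1.312/1.640 = 0.80; s′ = 0.5 gives 1.402/1.730 = 0.81.
- Absolute rates fall by about 8% to 18% over these cases, and by 0% if the off-IMP rate equals the on-IMP rate.
- Unequal stopping with s′ = 0: 20% Toujeo against 30% comparator gives 1.408/1.640 = 0.86. The reverse gives 1.312/1.760 = 0.75.

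**The case against.** The strongest reply is that this is loose wording. SAP 1.1 labels Visit 4 the end-of-treatment visit and, for patients who leave the trial early, records why treatment stopped. Protocol 6.2.1 does the same. On that reading, trial completion means end of treatment and nothing conflicts. This is plausible, but the text does not say it, and the remedy would still be to correct the sentence.

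A second reply is that SAP 2.4.5 may be what is programmed. SAP 2.4.5.1 limits hypoglycemia analyses to the TEAE period, and SAP 2.5.3 treats the TEAE period and the 12-month on-treatment period as one thing. This stands, so the consequences above are conditional. Under SAP 2.4.5 the Day 100 event is post-treatment at both locks.

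Third, a window to trial end may be wanted in a pragmatic trial, and counting switched insulin in the 6-month window matches the actual-arm rule in SAP 2.3.2. Either choice can be defended if it is stated and applied throughout. SAP 2.1.4 already has an on-study observation period for follow-up to trial end.

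A reader might also infer that the SAP changed the protocol's rule without declaring it, since SAP 1.5, "MODIFICATIONS TO THE STATISTICAL SECTION OF THE PROTOCOL", does not list the change and SAP 1.6 is marked not applicable. The documents do not establish this. The rule in the protocol's statistical section (11.4.3) is carried over almost unchanged in SAP 2.4.5, and Protocol 9.2.3 lies outside that section. An internal SAP inconsistency explains the texts equally well.

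**Conclusion.** The conflict is real, and the phrase in SAP 2.1.4 is the one out of line. Severity is minor to should-fix. The day counts rest only on first dose on Day 1 and follow-up to Day 360, which the protocol encourages but does not guarantee. The arm-level figures rest on assumed stopping and event rates.

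The 12-month definition affects only 12-month-lock safety output in patients who stop IMP early. The separate 6-month limit matters only for patients who switch basal insulin. The SAP calls its safety analysis essentially descriptive. With equal stopping, an illustrative rate ratio of 0.80 becomes 0.80 to 0.81. It moves further only if stopping differs between arms and off-IMP rates differ from on-IMP rates.

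Three stronger readings are not supported:
- That the primary result is at risk. The primary and composite endpoints use the ITT population and the randomized periods (SAP 2.4.4). The on-treatment sensitivity analysis uses the window in SAP 2.1.3, which is tied to last IMP.
- That the SAP as a whole adopts the longer window and SAP 2.4.5 is the stray sentence. The other sections only name the period.
- That on-treatment deaths are counted to trial end. SAP 2.1.4.4 refers to the on-treatment period without saying which one.

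**What to change.** In SAP 2.1.4:

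1. End the 12-month on-treatment period one day after last dose.
2. State one definition of last dose, either last IMP or last basal insulin including after a switch. Use it in the 6-month window, the 12-month window, the start of the post-treatment period and SAP 2.4.5, so that the periods do not overlap. The Month 7-12 period is then empty for patients who stopped before Month 6, and no separate rule is needed.
3. If follow-up to trial end is wanted, report it separately under the on-study observation period already defined there.
4. If any definition that departs from the protocol is kept, such as last insulin in place of last IMP, list it in SAP 1.5.

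The cost is SAP wording and the period flags in the analysis programs. No new data are needed.

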2.1.4.1 Hypoglycemia variables

Hypoglycemia observation periods

- Pre-treatment hypoglycemia events are events that occur during the pre-treatment period,
- Treatment-emergent hypoglycemia events are events that occur during the 12-month on-treatment period,
 - The 6-month treatment-emergent hypoglycemia events are events that occur during the 6-month on-treatment period,
- Post-treatment hypoglycemia events are events that occur during the post-treatment period.

Hypoglycemia endpoints will be classified in categories after events have been characterized using ADA Working group (2). More specifically, the following variables will be analyzed:

- Incidence and rate of documented symptomatic (BG \leq 70 mg/dL) or severe hypoglycemia (24 hour and nocturnal) from baseline to 6 and 12 months,
- Incidence and rate of documented symptomatic (BG <54 mg/dL) or severe hypoglycemia (24 hour and nocturnal) from baseline to 6 and 12 months, and,
- Incidence and rate of severe hypoglycemia (24 hour, per ADA definition) from baseline to 6 and 12 months.

Nocturnal hypoglycemia is defined as any hypoglycemia of the above categories that occurs between 00:00^{AM} and 05:59^{AM} hours, regardless whether patient was awake or woke up because of the event. Daytime hypoglycemia is defined as any hypoglycemia of the above categories that occurs between 6:00^{AM} to 23:59.

For each class of hypoglycemia as defined in [Appendix A](#), documented hypoglycemia will be analyzed in addition to the threshold of plasma glucose of less than or equal to 70 mg/dL (3.9 mmol/L), by using a threshold of plasma glucose of <54 mg/dL (3.0 mmol/L).

Patients are dispensed:

- A Bluetooth enabled study glucometer,
- E-diary,
- And Low Blood Glucose Event (LBGE) paper back-up page.

For all self-measured plasma glucose (SMPG) equal to or less than 70 mg/dL (or equivalent) LBGE symptoms, patients are instructed to complete:

- A hypoglycemia page in the e-diary,
- Or paper back-up page.

Hypoglycemic events will be transferred from the glucometer to a web based portal that serves as an electronic source document. Some hypoglycemic events may be recovered from paper source such as the hypoglycemia back up report or the patient paper diary. In all cases, the source will be reviewed by the site and manually entered into the CRF.

